In addition, while in the ICU all study subjects will be monitored with a non-invasive respiratory monitor (Expiron) to determine respiratory rate, tidal volume, minute volume and breathing pattern for up to 96 hours. This monitoring will aid in

detection of respiratory depression and add additional safety to the trial. This device measures chest expansion by thoracic impedance and is FDA approved.

Supplemental oxygen will be provided to maintain a peripheral oxygen saturation of 90% or greater.

Injections will be performed by trained trauma / critical care physicians. Training prior to initiating the study will include familiarization with the standardized procedure as described below, which will be documented in study records. Patients will be monitored by bedside nurses before, during, and after the block procedure. Standard inpatient cardiac arrest carts will be immediately available before, during, and after the block procedure.

A 20-mL vial will be obtained from IDS Pharmacy that either contains liposomal bupivacaine (266 mg in 20-mL) or 0.9% sodium chloride. Patients will be positioned either sitting up or in logroll/decubitus position. Rib fractures will be noted from previously obtained CT scan of the chest from initial trauma evaluation. The thoracic posterolateral area will be prepped and draped in sterile fashion. After aspiration to prevent intravascular injection, 1 mL of liposomal bupivacaine will be injected with a 25-G needle just below each affected rib by the intercostal neurovascular bundle in a posterior but not paravertebral position or 0.9% saline (as placebo control) will be injected with a 25-G needle in the subcutaneous space just superficial to each affected rib to minimize risk of placebo-injection complications. Optimal regional blockade will include the rib immediately above the most superior and the rib immediately below the most inferior fractured rib.

Regional blockade will only be performed once per patient enrolled in the study and at one injection site per fractured rib. Patients will only be enrolled once per acute traumatic event and admission.

If a patient enrolled in the study should have an adverse event during the course of intercostal rib block administration and the reaction is severe or life-threatening, then the patient will be withdrawn from the study and no further injections will be administered, regardless of how many injections were originally planned.

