A chest xray will be obtained as clinically indicated following the procedure if there is concern for the development of pneumothorax.

Self-reported pain will be measured using the verbal NRS, a 0-10 ordinal scale (e.g., 0 = "no pain"; 10 = "worst pain imaginable").²⁷ Breakthrough opioid dosing

will be guided by a formal inpatient analgesia protocol. Pain assessments will occur every 6 hours or per standard of care for the appropriate setting (e.g., intensive care unit, trauma ward) for the first 96 hours. All opioid dosing will be converted to oral morphine equivalents for comparison purposes. Time to first breakthrough opioid dose will be recorded. Incentive spirometry will be used and assessed and recorded by respiratory therapist, with adjunct inspiratory assistance (e.g., EzPAP) applied per our institutional volume expansion protocol.

Follow-up will occur daily by study coordinators and trauma service physicians for the first 96 hours after block procedure, then daily by the trauma service physicians for 14 days or until discharge from the hospital if it occurs earlier.

Standard of care analgesia regimen on the trauma service will be provided to all patients enrolled in the study, regardless of liposomal bupivacaine or placebo injection. This regimen will be per the Trauma acute multimodality pain management protocol (Appendix).

Typical escalation of analgesics provided for these patients, as deemed medically appropriate based on age and comorbid medical conditions, includes (in order of addition to regimen):

- Acetaminophen, oral or enteral
- NSAIDs, ibuprofen or ketorolac
- Lidocaine 5% transdermal patch
- Oral or enteral tramadol
- Oral or enteral hydrocodone or oxycodone
- IV morphine or hydromorphone, intermittent dosing
- Patient controlled analgesia morphine or hydromorphone
- Long-acting narcotics, including methadone, oxycodone ER, or morphine ER
- Neuromodulating adjuncts, including gabapentin or pregabalin
- Epidural analgesia catheter placement

During this time all adverse events will be recorded. Subjects who experience serious adverse events will be followed until the event resolves. If necessary these patients will be followed up by weekly phone calls as well as at the standard of care clinic visit two weeks post-discharge.

Randomization

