Following informed consent, patients will undergo 2x1 block randomization to ensure equal allocation to each intervention group. Randomization will be performed by study personnel and will be blinded as there will be placebo injections for patients randomized into group two and the same number of injections would be used regardless of intervention arm.

Data Collection:

Verbal NRS, pain assessment data, opioid use, and time to first opioid breakthrough dose will be collected as previously described. Portable spirometry will be used daily to objectively and serially assess lung function. Additional data collection points include patient sex, age, weight, body mass index, body surface area, injury severity score, chest abbreviated injury score, and ICU and hospital length of stay. Safety will be evaluated by the occurrence of *a priori* serious adverse events. Costs will be evaluated utilizing hospital and pharmacy databases.

Schedule of subject identification and data collection

Subjects will be identified based on inclusion criteria at the time of admission to the trauma service following evaluation in the emergency department. Subjects meeting inclusion criteria will be enrolled within 6 hours of admission. Vitals monitoring will occur during the intercostal nerve block procedure and continue by telemetry for the next 96 hours or until hospital discharge, whichever occurs first.

7. Specimen collection:

No serum assays are necessary for this study and will not be collected.

8. Potential Benefits:

Blunt chest wall trauma remains a common injury seen in non-intentional injury-related deaths. It accounts for nearly 10% of trauma-related emergency department visits worldwide and is associated with high morbidity and mortality. This morbidity and mortality are influenced by the pain experienced by these events which can involve rib or sternal fractures as instigating stimuli.

Uncontrolled analgesia following rib fractures can result in intubation, pneumonia, prolonged length of stay, and death. Achieving adequate pain control in native airway patients prevents clinical challenges. Multimodal analgesia regimens are necessary to optimize patient outcomes and prevent untoward effects of opioid analgesia (e.g., hypotension; bradycardia; central nervous system depression; respiratory depression).

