 - c. Median time to first breakthrough opioid rescue dose
 - d. Incentive spirometry serial volume capacity
 - e. ICU LOS
 - f. Hospital LOS
 - g. Use of additional analgesia adjuncts
 - i. Epidural catheter
 - ii. Non-opioid analgesics (e.g., non-steroidal anti-inflammatory drugs; gabapentin; pregabalin; carbamazepine; ketamine; acetaminophen)
- 2) Perform a cost-effectiveness analysis
- 3) Calculate dose and exposure of lidocaine or bupivacaine over time from Lidoderm patches, intercostal nerve blocks, or epidural catheters

Statistical analyses will be performed using SAS. An intention-to-treat model will be used for data analysis. Patients randomized into the treatment arm will be included in the primary outcome analysis. Patients withdrawn from the study will have data included up to the point of withdrawal. Nominal data will be reported using frequencies of occurrence and proportions as appropriate. Continuous data will be reported using means and standard deviations or medians and

interquartile ranges as appropriate per distribution. Hypothesis testing for nominal data will be performed using the Fisher's exact test or chi square test as required based on sample size. Continuous data will be compared using student's t-test/ANOVA or rank sum/Kruskal-Wallis ANOVA for normally distributed and non-normally distributed data, respectively as appropriate. A p-value < 0.05 will designate statistical significance. Costs associated with the cost-effectiveness analysis will be pulled from hospital and pharmacy databases.

Given the pilot nature of the study, a total of 200 patients will be enrolled. Assuming a 96-hour requirement of 250-mg oral morphine equivalents (approximately 12.5-mg IV hydromorphone), we anticipate a 20% reduction to 200-mg oral morphine equivalents (approximately 10-mg IV hydromorphone) resulting in an expected difference in means of 50 mg and an anticipated standard deviation of 50 mg. To achieve an 80% power with an alpha of 0.05 for this primary outcome, the goal enrollment is 200 patients.

12. Data storage and confidentiality (include sample storage if applicable)

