- c. Patients with known or suspected atrioventricular nodal blockade process requiring cardiology evaluation and/or pacemaker placement
- d. Hemodynamic instability (defined as a new intravenous vasopressor or inotrope requirement [e.g., norepinephrine; epinephrine; phenylephrine; dobutamine; milrinone] or a mean arterial pressure < 55 mmHg)
- e. Signs of active myocardial ischemia or non-ST elevation MI
- f. Patients with greater than 20 rib fractures (20-mL vial [266-mg dose]; 1-mL [13.3 mg] per rib)
- g. Weight < 50 kg or > 150 kg
- h. Pregnancy as defined by urine pregnancy test in all females of child-bearing potential
- i. Incarceration
- j. Inability to obtain informed consent
- k. Severe traumatic brain injury, GCS <8

Patients will be followed for outcome assessment during hospitalization through discharge.

14. Consenting process and plan

Patients will be identified as previously described and permission to consent per the trauma team attending will be obtained prior to administration of consent. Study personnel will administer consent in the patient's room. Patients who meet inclusion and exclusion criteria will be eligible for consent. Informed consent will be obtained prior to randomization into treatment arms. Patients unable to give consent will have LAR or next of kin consented. LAR must show proof of health care POA or court document. A copy of the documents will be kept with the

consent form. Next of kin is a person who may act as LAR without a document granted by court. Next of kin will be determined by team social workers' note. The order in which the next of kin may act as LAR is: spouse, parent, adult son or daughter, adult brother or sister. If next of kin available at the time of consent cannot agree, the person cannot participate in the research. Investigators will be available seven days a week and will continue correspondence with subjects throughout the study for up to 7 days or until hospital discharge, whichever comes first.

Subjects can withdraw from the study at any time per their desire or may be withdrawn at the discretion of the trauma team. Subjects will be withdrawn as appropriate based on any adverse event that may occur as described above in Section 9. Any subject who withdraws will be placed on standard of care.

15. Compensation:

Patients will not receive any compensation for research involvement.

16. Subject costs:

There are no additional costs to subjects.

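### Section 11 leaves collected prognostic data out of the primary comparison (a precision loss only) and gives time to first breakthrough dose no survival method, no rule for undosed patients and no assigned observation window

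*Combined protocol and SAP*

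**What the plan says.** **Tests.** Section 11 (Data Analysis) gives one rule for every continuous outcome: "Continuous data will be compared using student's t-test/ANOVA or rank sum/Kruskal-Wallis ANOVA" "for normally distributed and non-normally distributed data, respectively as appropriate". It names no covariate or stratification factor. The primary endpoint is opioid requirement in morphine equivalents; the 96-hour window appears in the sample-size paragraph, with means of 250 and 200 mg and an SD of 50 mg.

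**Baseline data.** Section 6 (Data Collection) lists "patient sex, age, weight, body mass index, body surface area, injury severity score, chest abbreviated injury score". Section 6 (Intervention) adds: "Rib fractures will be noted from previously obtained CT scan of the chest from initial trauma evaluation". None of these has a stated role in the comparison of arms.

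**Breakthrough dose.** The Section 11 secondary endpoints include "Median time to first breakthrough opioid rescue dose". Section 6 says only: "Time to first breakthrough opioid dose will be recorded". The documents give no time origin, survival method or censoring rule. The nearest rule, in Section 11, is that a withdrawn patient's data count until withdrawal, within an intention-to-treat analysis.

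**Follow-up.** Several periods are stated:
- Section 6: 96 hours for pain assessments and coordinator visits, "then daily by the trauma service physicians for 14 days or until discharge from the hospital if it occurs earlier".
- Section 13: "Patients will be followed for outcome assessment during hospitalization through discharge".
- Section 14: investigator contact for up to 7 days or until discharge.

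None is tied to the breakthrough endpoint.

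**The concern.** Opioid use after chest trauma plausibly varies with the number of broken ribs, injury severity, age and weight. All are known before injection. An unadjusted comparison leaves whatever variance they explain in the error term, so the interval for the primary effect may be wider than it need be. Choosing between t-test and rank-sum after seeing the distribution also leaves open whether the headline result is a difference in means or a comparison of ranks.

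For the breakthrough endpoint, some patients may have no dose time because they withdrew, were discharged or never needed a dose. Entry requires an anticipated stay of only 72 hours, so discharge before 96 hours is foreseeable. The analyst must then leave these patients out, rank them at a ceiling or censor them. Those choices can give different medians and p-values, and the plan does not choose.

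**Working it through.** **1. The plan's own figure.** Section 11 gives a difference of 50 mg, SD 50 mg, alpha 0.05 (two-sided assumed), 80% power and 200 patients. Per arm, n = 2 × (1.960 + 0.842)² × (50/50)² = 15.7, so 16 per arm or 32 in total (34 with a t-based calculation). The 200 is not reproduced. That is a separate matter, but it means that at 100 per arm the unadjusted test already has power above 99.99%.

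**2. Half-width of the primary 95% interval.**
- Unadjusted: SE = 50 × √(2/100) = 7.07 mg, and 1.972 × 7.07 = 13.9 mg.
- Adjusted for four covariates: the variance is multiplied by (1 − R²) and by 1 + 4/193 = 1.0207, the average cost of estimating four coefficients with 200 patients. Half-width = 1.972 × 7.07 × √[(1 − R²) × 1.0207]. Equivalent unadjusted sample size = 200 / [(1 − R²) × 1.0207].

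| R² (assumed) | Half-width, mg | Equivalent unadjusted N |
|---|---|---|
| 0 | 14.1 | 196 |
| 0.1 | 13.4 | 218 |
| 0.2 | 12.6 | 245 |
| 0.3 | 11.8 | 280 |

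**3. Power.** At SD 50 mg it exceeds 99.99% in every row. Visible gains need a much larger SD. With the same covariate cost and R² of 0.1 to 0.3, power rises from 94% to 96–99% at SD 100 mg, and from 80% to 83–91% at about 126 mg, the SD at which 200 patients would give 80% power.

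**4. Behaviour of ANCOVA in mg.** In simulation (4,000 replicates, normal and right-skewed totals, R² 0 to 0.3) type I error was 4.5–5.6%. With lognormal totals, a control SD of 125.6 mg and a 20% reduction, power of ANCOVA against the unadjusted rank-sum was 0.870 v 0.895 (R² 0), 0.898 v 0.900 (0.1), 0.927 v 0.897 (0.2) and 0.952 v 0.900 (0.3).

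**5. Breakthrough dose: what leaving out undosed patients would do.** Assumptions, none from the documents: exponential times, hazard ratio 0.65, follow-up ending at 96 h. With event rate λ, the median among dosed patients is −ln(1 − F/2)/λ, where F = 1 − exp(−96λ).

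| Control median, h | Undosed at 96 h, control v active | True difference in medians, h | Difference among dosed only, h |
|---|---|---|---|
| 6 | about 0% | 3.2 | 3.2 |
| 12 | 0.4% v 2.7% | 6.5 | 5.8 |
| 24 | 6% v 16% | 12.9 | 6.9 |
| 36 | 16% v 30% | 19.4 | 6.0 |

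Lognormal times (median ratio 1.5, log-SD 1) show the same pattern: 3.0 becomes 2.9, 6.0 becomes 5.2, 12.0 becomes 7.7 and 18.0 becomes 8.3 h. With a 14-day window (336 h) for everyone, the exponential 24 h case moves only from 12.9 to 12.8 h, so the choice of window matters.

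**6. Power under three handling rules.** With exponential times, hazard ratio 0.65, 100 per arm, a 96 h end and 5% to 30% of controls undosed, power falls from 39% to 10% if undosed patients are left out, from 73% to 64% if they are set to 96 h in a rank-sum, and from 82% to 68% with a log-rank test.

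**7. Ceiling rank-sum against log-rank.** Over control medians of 6 to 36 h, log-rank power is 77–86% against 71–74% under exponential times, but 74–75% against 78–81% under lognormal times. With 10% v 30% of patients leaving between 66 and 96 h, the ceiling rank-sum rejects a true null 4.6–5.3% of the time.

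**The case against.** **On the primary outcome.** The unadjusted comparison is valid in a randomised trial, and the gain in half-width is only 0.6 to 2.2 mg against an expected effect of 50 mg. It rests on an R² that the documents do not supply. Rib-fracture count is read from CT but is not in the Section 6 data list. With skewed totals and weak covariates, the rank-sum does as well or slightly better. All of this stands, and it is why the point is a low-cost improvement and not an error. A reader might infer bias or inadequate power from the lack of adjustment; the documents support neither.

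**On the breakthrough endpoint.** A reader might infer three stronger things, none of which holds.
- That no end of follow-up is stated. Several are; they differ, and none is assigned to this endpoint.
- That the listed tests cannot handle undosed patients. A rank-sum with those patients at a common ceiling is usable and keeps its error rate in the scenarios checked. The plan simply does not say that this will be done.
- That the plan leaves undosed patients out. It never says so, and its intention-to-treat wording and withdrawal rule point the other way. The shrunken medians above show what that choice would do; they do not predict this trial's result.

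Planned means of 200 to 250 mg with an SD of 50 mg also suggest that nearly everyone will receive opioids, so few patients may be undosed.

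**Conclusion.** Both parts hold in limited form, as points to consider.

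The primary analysis is valid but less precise than it could be. The half-width would fall from 13.9 mg to about 13.4, 12.6 or 11.8 mg for an assumed R² of 0.1, 0.2 or 0.3, and would rise to 14.1 mg if the covariates explained nothing. Power is not at issue at the stated SD.

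The breakthrough endpoint lacks a survival method, a time origin, a rule for undosed patients and an assigned window. The effect ranges from negligible, if nearly all patients are dosed early, to about half or more of the difference in medians, if many are undosed when follow-up ends and are left out. The documents give no event or exit rates, and their planning means favour the milder end. Neither general type I error inflation nor a general power advantage for the log-rank test is claimed.

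**What to change.** **Primary.** Prespecify ANCOVA of 96-hour oral morphine equivalents in mg, the scale of the sample-size calculation, on arm, number of fractured ribs, chest AIS, age and weight. Report the mean difference with its 95% CI, and keep the unadjusted rank-sum as sensitivity analysis.

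**Breakthrough dose.** Use Kaplan-Meier medians with a log-rank test over one stated window, for example 96 hours to match the primary outcome. State one time origin that also covers patients randomised but not injected; randomisation would do so. Censor at withdrawal, discharge or the end of the window. Because discharge may be related to pain, add a sensitivity analysis that ranks undosed early discharges at the ceiling.

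**Cost.** SAP wording, a few lines of SAS and one data field for the rib count already read from CT. It should be settled before outcome data by arm are seen. The downsides are a half-width of 14.1 mg instead of 13.9 mg if the covariates are uninformative, a possible small loss against the rank-sum with skewed totals and weak covariates, and some loss of log-rank power if hazards are not proportional. Adjustment does not settle how 96-hour totals cut short by early exit are handled; that needs its own rule.

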The primary purpose of this pilot study is to compare opioid requirements between groups receiving intercostal liposomal bupivacaine to standard of care for acute traumatic pain related to blunt chest wall trauma with resultant rib and/or sternal fractures. Pain scores will be evaluated using the NRS (Appendix). Uncontrolled analgesia following rib fractures can result in intubation, pneumonia, prolonged length of stay, and death. Achieving adequate pain control in native airway patients prevents clinical challenges. Multimodal analgesia regimens are necessary to optimize patient outcomes and prevent untoward

effects of opioid analgesia. Liposomal bupivacaine offers a novel therapy that may revolutionize pain management in patients with rib fractures. Pain control with one injection may provide analgesia for up to 96 hours through a unique mechanism of action and site of application. Overall, the combination of a nonopioid analgesic, liposomal bupivacaine, with standard of care may lead to improved analgesia with fewer adverse effects. Specific aims include to 1) compare opioid requirements (in morphine equivalents) between patients with blunt chest wall trauma and rib and/or sternal fractures receiving liposomal bupivacaine versus standard of care; 2) compare clinical outcomes and treatment failures including development of pneumonia, median patient analgesia score using verbal NRS, median time to first breakthrough opioid dose, IS ability, ICU LOS, hospital LOS, and use of additional analgesic adjuncts; 4) and to perform a cost-effectiveness analysis

5. Background:

Background and Significance

Blunt chest wall trauma remains the second most common injury observed in non-intentional injury-related death in the U.S.A. and accounts for 10% of trauma-related emergency department visits worldwide.¹⁻³ Current literature has identified high morbidity and mortality rates for patients suffering from blunt chest wall trauma, with mortality ranging from 4 to 20%.^{2,4} The prevalence of rib fractures among blunt chest wall trauma patients requiring hospital admission is 4 to 10%.⁵ One of the most prominent contributing factors to blunt chest wall trauma morbidity is pain.⁶⁻⁸ The management of resultant pain serves as a core intervention in managing these patients.⁸

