emergency medicine and surgery practitioners are familiar with intercostal blocks for placement of tube thoracostomy. Intercostal blocks do not require additional training, as would be done in the setting of a pain medicine fellowship, and do not incur the risks of hypotension associated with epidural catheters. Additionally, intercostal and paravertebral blocks carry similar risks of pneumothorax or intercostal neurovascular bundle injury.

Study design:

This is an investigator-initiated, single-center, prospective, double-blinded, placebo-controlled trial funded by the United States Air Force. Multi-system, adult trauma patients greater than or equal to 18 years of age admitted to the University of Cincinnati Medical Center (UCMC), an urban American College of Surgeons-verified Level 1 trauma center with more than 3500 annual trauma admissions annually will be identified by the research team. Patients will be screened and those who meet all inclusion/exclusion criteria will be approached for informed consent by study personnel in their rooms. Informed consent will be obtained prior to enrollment and any study procedures are done. Patients will then receive either receive 1 mL of liposomal bupivacaine just below each affected rib or 0.9% sodium chloride peri-intercostal subcutaneous injection (as placebo control) via a 25-G needle. Goal enrollment is 200 patients with 100 patients in each group. Patients included in the study will be followed during inpatient hospitalization through discharge.

6. Research data collection/study procedures:

Intervention

Patients will be identified on admission and will be screened by inclusion/exclusion criteria. After informed consent is obtained they will be randomized into one of two possible groups:

- a. Liposomal bupivacaine intercostal (group 1; interventional)
- b. 0.9% sodium chloride peri-intercostal subcutaneous (group 2; placebo-control)

Patients will be placed on continuous monitoring of heart rate, EKG, and pulse oximetry. Blood pressure and respiratory rate will be measured every 5 to 10 minutes during the procedure and every at least 15 minutes for the first hour after the procedure. All patients undergoing injection will remain on heart rate, EKG, and pulse oximetry monitoring by telemetry for 96 hours following injection.

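### The stated inputs (difference 50 mg, SD 50 mg, 80% power, alpha 0.05) need 34 patients by a two-sided t-test, not 200; with 200 patients they give more than 99.99% power

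*Combined protocol and SAP*

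**What the plan says.** Section 11 (Data Analysis) gives the whole calculation in its last paragraph. The 96-hour opioid requirement is taken as 250 mg oral morphine equivalents, falling by 20% to 200 mg, which gives an "expected difference in means of 50 mg and an anticipated standard deviation of 50 mg". It then concludes: "To achieve an 80% power with an alpha of 0.05 for this primary outcome, the goal enrollment is 200 patients". The Study design text in section 5 splits this total: "Goal enrollment is 200 patients with 100 patients in each group".

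The same paragraph in section 11 opens with a different basis for the number: "Given the pilot nature of the study, a total of 200 patients will be enrolled". Section 4 (Purpose of Study) also calls the trial a pilot: "The primary purpose of this pilot study is to compare opioid requirements between groups".

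The significance criterion is "A p-value < 0.05 will designate statistical significance", without sidedness. The tests named for continuous data are the t-test or the rank-sum test, depending on distribution. No dropout allowance is given, and the paragraph gives no source for the SD.

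**The concern.** The paragraph prints every input that a two-group comparison of means needs, so the sample size can be checked directly. A difference equal to one SD is a large effect, and 80% power for it takes a few dozen patients. A total of 200 is out of proportion.

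This is the only power statement for the primary outcome. If the inputs are right, the paragraph presents as necessary for 80% power a trial that is 166 patients larger than that target requires, and it gives no quantified reason for randomising the rest. If an input was misstated, the real power is unknown to the reader and depends on which input changes and by how much. The paragraph does not allow a reader to tell these situations apart.

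**Working it through.** **Inputs**

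- From section 11: difference Δ = 250 − 200 = 50 mg; SD σ = 50 mg; power 80%; alpha 0.05.
- From section 5: 100 per group.
- Assumed: two-sided test, because sidedness is not stated.

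**Standardised effect.** d = Δ/σ = 50/50 = 1.0.

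**Attempt to reproduce 200**

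- Normal approximation: n per group = 2(z₀.₉₇₅ + z₀.₈₀)²/d² = 2(1.960 + 0.842)²/1² = 15.7, so 16 per group and 32 in total.
- t-test (noncentral t): n per group = 16.71, so 17 per group and 34 in total. Power is 80.7% at 17 per group and 78.1% at 16.

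The stated total is 200/34 = 5.9 times as large, and the excess is 200 − 34 = 166 patients.

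**Other readings at d = 1**

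| Reading | Total N |
|---|---|
| One-sided 0.05, t-test | 28 (14 per group) |
| 2:1 allocation, t-test | 39 (13 + 26) |
| Rank-sum at worst-case efficiency 0.864 | 40 (16.71/0.864 = 19.3, so 20 per group) |
| 90% power | 46 (23 per group) |
| 99% power | 76 (38 per group) |
| 34 inflated for 20% dropout | 43 (34/0.8 = 42.5) |

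The 2:1 row is there only because the Randomization text says "patients will undergo 2x1 block randomization to ensure equal allocation to each intervention group"; that sentence and section 5 both point to equal groups. Combining 2:1 allocation, worst-case rank-sum efficiency and 20% dropout gives 12.45/0.864 = 14.4, so 15 + 30 = 45, and 45/0.8 = 56.25, so 57. Turning 34 into 200 by dropout alone would take a loss of 1 − 34/200 = 83%.

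**Power at the planned size.** With 100 per group and d = 1, the t-test has power 0.9999998. If half of each group were lost (50 per group), it would still be 0.9986.

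**Working back from 200 and 80%.** With 100 per group, the effect detectable at 80% power is d = 0.398. That corresponds to either:

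- an SD of 50/0.398 = 125.6 mg with the 50 mg difference; or
- a difference of 0.398 × 50 = 19.9 mg with the SD of 50 mg, which is 19.9/250 = 8% of the control requirement rather than the stated 20%.

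**Sensitivity to the SD.** Power for a 50 mg difference with 100 per group, t-test. SDs above 50 mg are assumed for illustration and are not in the documents.

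| SD (mg) | Power |
|---|---|
| 50 | >99.99% |
| 75 | 99.7% |
| 100 | 94% |
| 125 | 80% |
| 150 | 65% |
| 200 | 42% |

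**The case against.** Four points can be made for the plan.

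First, the sentence does not say that 200 is the minimum or that power is exactly 80%; on the stated inputs 200 patients do achieve at least 80%. That is true of the wording. But the paragraph lays out a difference, an SD, an alpha and a power target and then gives 200 as what they lead to. Reading it as a lower bound does not explain where 200 came from.

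Second, a separate reason is present, namely that this is a pilot. This stands in part: it would be unfair to say that no other reason is mentioned. But it carries no calculation and does not explain why a pilot needs 200. The secondary outcomes, the cost-effectiveness analysis or the percentage-based stopping rules in section 10 might call for more than 34 patients, but the protocol never links them to 200.

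Third, 34 depends on a two-sided t-test. It does, and the assumption should be stated. The alternatives change the figure modestly and none comes near 200.

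Fourth, at face value the error runs towards excess power and leaves the endpoint, alpha, tests and enrolment unchanged. This also stands: nothing here shows the trial to be underpowered. Power for 50 mg falls below 80% only if the SD exceeds about 125 mg, 2.5 times the stated value, and nothing in the documents supports an SD of that size. The harm is that the justification for the sample size is wrong and cannot be checked.

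**Conclusion.** The concern holds and must be fixed. On the printed inputs, 80% power needs 34 patients (17 per group), and 200 patients give more than 99.99% power. The result assumes a two-sided two-sample t-test with equal groups and no dropout. Relaxing those assumptions one at a time, within ordinary limits, moves the total only between 28 and 43, and combining the unfavourable ones reaches about 57.

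At least one element of the statement (difference, SD, power, or the link to 200) is therefore misreported. The documents do not show which, or whether 200 was set on other grounds. The finding is not that 200 is too few, nor that 200 cannot be justified; it is that this paragraph does not justify it.

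**What to change.** Rewrite the sample-size paragraph in section 11. State the SD and its source, the sidedness, the test on which the calculation is based, and any dropout allowance. Then take one of two routes.

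- **(a) The 50 mg difference and 50 mg SD stand.** State that 100 per group gives more than 99.9% power for 50 mg and 80% power for about 20 mg. Remove the claim that 80% power calls for 200. Give the separate reason for enrolling 200, in terms of what the pilot, secondary or safety aims need.
- **(b) The SD or the difference was misstated.** Correct it, give its source, and state the power that 200 patients provide.

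Under either route, a short table of power at 100 per group over a range of SDs, for example 50 to 200 mg, would be useful but is optional.

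The cost is one paragraph of rewording and no additional patients. Under (a) the sponsor has to justify about 166 patients beyond the power target. Under (b) the stated power may become less favourable if the SD is revised upward.
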